## **3. Research Design and Methods**

### **Prospective Validation of a Multimodal Imaging Large Model**

#### **(I) Study Design Type and Methodology**

This study is a single-center prospective observational study, aiming to conduct prospective validation and optimization of the established medical multimodal large model based on real-time collected clinical multimodal data (imaging, medical records, laboratory tests, reports, etc.). No additional interventions will be imposed on patients' diagnosis and treatment processes during the study; relevant data will only be collected synchronously during routine clinical examinations and diagnostic procedures, making it a non-interventional, minimal-risk prospective study.

During the study period, all newly diagnosed cases meeting the inclusion criteria will be consecutively enrolled. The research team will conduct prospective inference and performance validation of the multimodal medical large model based on imaging findings, EMR text, and laboratory test data, systematically evaluating the model's performance in tasks such as disease diagnosis, lesion localization, and report generation. Study results will be compared with clinicians' actual diagnostic conclusions and pathological gold standards to verify the model's generalization ability and clinical applicability in real-world scenarios.

The overall study protocol includes the following phases:

1. **Case recruitment and data collection:** Patients undergoing imaging examinations in the hospital will be consecutively recruited according to pre-defined inclusion criteria. Study data are derived from routine clinical workflows, covering imaging data, EMRs, laboratory results, and radiology reports. All data will undergo de-identification and quality control before being entered into the study database, with only the minimum necessary information retained.

2. **Model application and inference:** The research team will deploy the multimodal model in the hospital's secure computing environment. For each enrolled patient, the model will automatically generate disease predictions, lesion localization results, and diagnostic reports based on their imaging data and corresponding clinical text.

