3. **Clinical comparison and result documentation:** The model outputs will be subject to double-blind evaluation by radiologists and clinicians from relevant departments, compared with the final pathological or clinically confirmed results, and the accuracy, consistency, and interpretability of model predictions will be documented.

4. **Model iteration and continuous validation:** On the premise of ensuring ethical and privacy compliance, the research team will use newly collected data for continuous model fine-tuning and validation, analyzing its stability and robustness across different disease types, devices, and operational conditions.

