## **(III) Patient Inclusion, Exclusion, and Withdrawal Criteria**

### **Inclusion Criteria**

1. Adult patients aged  $\geq 18$  years;
2. Undergoing imaging examinations (CT, MRI, ultrasound, etc.) in the hospital during the study period;
3. Examination items corresponding to the disease types or systems focused on by the study (hepatobiliary and pancreatic system);
4. Possessing at least complete imaging data and radiology diagnostic reports, with relevant medical record information as supplementary modalities;
5. Patients or their legal representatives signing an informed consent form, agreeing to the use of their de-identified data for scientific research model validation;
6. Case data passing quality review, with good imaging quality and standardized text records.

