#### **(IV) Detailed Research Protocol**

##### **Research Data Sources**

Data for this study are derived from patients undergoing routine clinical examinations in the hospital during the study period. Data collection is accomplished relying on the hospital's existing information systems, without imposing additional burdens on patients or interfering with diagnosis and treatment processes. All data are real-world multimodal information generated in routine clinical practice, mainly including:

- Medical imaging data from the Department of Radiology, covering original images and reconstructed sequences such as CT, MRI, and ultrasound, as well as manual annotations, masks, or structured descriptions, which serve as reference standards for model validation;
- Radiology diagnostic reports, including examination findings, diagnostic conclusions, and physician recommendations. All images undergo unified format conversion (e.g., DICOM to NIfTI) and quality assessment before being imported into the study database, with sequences containing artifacts or defects excluded;
- Text data from the electronic medical record system, including admission records, discharge summaries, progress notes, and surgical records. Prior to import, text data undergo automated de-identification to remove sensitive information such as names, hospital admission numbers, ID card numbers, and contact information, retaining only key clinical course points relevant to the research objectives;
- Structured laboratory data from the laboratory information system, including quantitative data such as complete blood count, biochemical indicators, tumor markers, and coagulation function, which are aligned with imaging examinations via timestamps to support cross-modal feature fusion and quantitative analysis of disease states in the model.

All research data undergo rigorous de-identification before being imported into the analysis environment, with only the minimum necessary information required for the study retained. Data collection and usage comply with the Personal Information Protection Law, Data Security Law, and the hospital's ethical requirements. All patients sign a written informed consent form prior to enrollment, explicitly agreeing to the use of their de-identified data for scientific research model validation and performance optimization. The entire research process is conducted under the approval and supervision of the IRB.

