#### **Sample Size Estimation Process**

The sample size for the prospective validation of this study is determined based on statistical power analysis. Assuming the model achieves an accuracy of approximately 85% in the disease diagnosis task, compared with an 80% accuracy rate of manual diagnosis, with an expected detectable performance difference of 5%, a significance level ( $\alpha$ ) set at 0.05, and a test power ( $\beta$ ) set at 0.2, approximately 500–600 cases per group are required according to the binomial distribution sample size calculation formula, with a total of 1000–2000 newly enrolled cases needed to meet statistical significance requirements.

Considering potential loss to follow-up or data disqualification during the prospective study, the final plan is to collect complete multimodal data (including imaging, reports, and laboratory results) from approximately 2000 patients for model validation and performance analysis. This sample size ensures the accurate evaluation of the model's stability, generalization ability, and consistency with expert diagnosis in real-world clinical scenarios at a 95% confidence level.

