#### **Statistical Analysis Procedures**

This study adopts intention-to-treat (ITT) analysis as the primary analytical strategy, conducting systematic statistical analysis on data from all enrolled cases. First, descriptive statistics are performed to summarize the baseline characteristics of patients, including age, gender, disease type, and imaging equipment source. Continuous variables are presented as mean  $\pm$  standard deviation or median depending on their distribution type, while categorical variables are expressed as frequencies. Inter-group differences are analyzed using appropriate statistical methods based on data characteristics: the t-test is used for normally distributed data, and the Mann–Whitney U test is used for non-normally distributed data.

In the analysis of primary outcome indicators, this study focuses on evaluating the model's performance in three core tasks: disease diagnosis, lesion localization, and report generation. For the disease diagnosis task, clinical final diagnosis or pathological results are used as the gold standard to calculate AUC, Sensitivity, Specificity, Accuracy, and F1-score, and receiver operating characteristic (ROC) curves are plotted to comprehensively assess the model's classification ability. For the lesion localization and segmentation task, expert annotations are used as references to calculate the Dice coefficient and Hausdorff distance, measuring the model's performance in lesion recognition range and boundary precision. For the report generation task, model-generated reports are compared with radiologists' reports at the text level, and natural language generation metrics such as BLEU, ROUGE, and CIDEr are used to evaluate language quality and semantic consistency.

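### The model is fine-tuned on the cohort that validates it, with no version lock, so the pooled primary metrics describe no fixed model and can be optimistic

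*Protocol*

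**What the plan says.** All references are to the Protocol.

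- **Aim** (section 3 (I)): the study is a "prospective validation and optimization of the established medical multimodal large model", so validation and optimization share one prospective cohort.
- **Scoring** (section 3 (I), phase 2): "For each enrolled patient, the model will automatically generate disease predictions, lesion localization results, and diagnostic reports". No version is named, and nothing is said about the order of scoring and fine-tuning.
- **Updating** (section 3 (I), phase 4): "the research team will use newly collected data for continuous model fine-tuning and validation".
- **Cohort** (section 3 (IV), Sample Size Estimation Process, repeated in section 4): complete multimodal data are to be collected "from approximately 2000 patients for model validation and performance analysis". No part is set aside for tuning.
- **Analysis set** (section 3 (IV), Statistical Analysis Procedures): "conducting systematic statistical analysis on data from all enrolled cases". Cases used for fine-tuning are not removed.
- **Development data** (section 4, Retrospective Study Phase): a separate set of 10,000–20,000 image-text pairs is already planned for fine-tuning.
- **Consent**: inclusion criterion 5 has patients "agreeing to the use of their de-identified data for scientific research model validation". Research Data Sources has them "explicitly agreeing to the use of their de-identified data for scientific research model validation and performance optimization".

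**The concern.** A validation study estimates how one defined model performs on patients it has not seen. Two conditions are needed: the model stays the same throughout, and no test case has helped to train it. Continuous fine-tuning on the validation cohort breaks the first condition and leaves the second unprotected.

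If the model changes during enrolment, a pooled AUC, accuracy, Dice or BLEU is an average over versions, weighted by how many patients each version happened to score. It is not the performance of the model that entered the study, nor of the one that leaves it. The stability analyses by device, disease type and population (secondary outcome 2) are exposed too: if case mix shifts over the year, a subgroup difference may be a version difference.

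If any case is scored by a version already trained on it, that case is no longer an independent test. Report generation is the most exposed task, because the radiologist's report is both the yardstick for the text metrics and a natural fine-tuning target.

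**Working it through.** **1. What the text fixes.** Set side by side, phase 2 scores every enrolled patient, phase 4 fine-tunes continuously on newly collected data, the sample size section gives all of about 2000 patients to validation, and the analysis section keeps all enrolled cases. No sentence names a lock date, a tuning/test split, a score-before-train rule, or the version behind the primary outcomes. No calculation is needed for this step.

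**2. Version mixing, even without leakage.** If version k scores a share w_k of the patients and has accuracy A_k, the pooled accuracy is Σ w_k·A_k. To illustrate with the protocol's two planning values (the equal split is an assumption): half the patients scored at 80% and half at 85% gives 0.5 × 0.80 + 0.5 × 0.85 = 82.5%. Neither version has that accuracy.

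**3. Possible leakage.** Inputs: the protocol plans for 85% model accuracy against 80% manual, a difference of 5 points. Let f be the share of cases scored by a version already trained on them, and a the accuracy on those cases. With true accuracy 80%, that is, no advantage:

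apparent accuracy = (1 − f) × 0.80 + f × a

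| f | a = 0.85 | a = 0.90 | a = 0.95 | a = 1.00 |
|---|---|---|---|---|
| 0.10 | 80.5% | 81.0% | 81.5% | 82.0% |
| 0.25 | 81.25% | 82.5% | 83.75% | 85.0% |
| 0.50 | 82.5% | 85.0% | 87.5% | 90.0% |

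Neither f nor a is in the protocol, and f = 0 is compatible with it. The table shows sensitivity to the assumptions; it is not an estimate.

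**4. What a small bias would do to a test.** Assume 2000 cases read by both model and physician, no true difference, discordance p_d = 0.20, and a two-sided 5% McNemar-type test. With upward bias b,

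P(significant in favour of the model) = 1 − Φ[(1.96·√(p_d/2000) − b) / √((p_d − b²)/2000)].

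| Bias b | p_d = 0.10 | p_d = 0.20 | p_d = 0.32 |
|---|---|---|---|
| 1 point | 0.29 | 0.17 | 0.12 |
| 2 points | 0.81 | 0.52 | 0.35 |
| 3 points | 0.99 | 0.85 | 0.66 |

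The nominal value is 0.025. The pairing and the discordance are assumptions.

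**5. Can the study afford a lock?** If the locked version scores every patient once, no cases are lost. If some patients were instead set aside for tuning, power to detect 85% against 80% with m paired test cases is Φ[(0.05·√m − 1.96·√p_d) / √(p_d − 0.0025)]:

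| Test cases m | p_d = 0.20 | p_d = 0.29 |
|---|---|---|
| 2000 | 0.999 | 0.986 |
| 1400 | 0.987 | 0.936 |
| 1000 | 0.944 | 0.837 |

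Under a paired analysis, even a set-aside is affordable. The stated 500–600 cases per group is not used here; whether it can be reproduced is a separate matter.

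**The case against.** The strongest reply is that the phases are numbered: the model runs on each patient, outputs are compared and documented, and only then does iteration follow. The text also speaks of prospective inference on data collected in real time. On that reading each case is unseen when scored, and there is no optimism from training on test cases. This stands. A reader might infer that cases are scored on their own training data and that the results are therefore optimistic, but the protocol does not say so. It allows that outcome without prescribing it. The reply does not remove version mixing, because later patients would still be scored by a model that earlier patients had changed.

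Second, the purpose given for phase 4 is stability and robustness, which fits a secondary outcome, and no sentence says that phase 4 outputs replace those of phases 2 and 3 in the primary metrics. That is fair. But the protocol refers throughout to one model and provides no separate frozen copy for the primary outcomes.

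Third, the accuracy assumed on reused cases has no source. The only tuning method described, for the retrospective phase, keeps most of the network frozen, so near-perfect recall cannot be presumed. This stands too: a reader might take the 25%/100% cell, which reproduces the whole planned advantage, as the expected bias, and nothing supports that.

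Fourth, a reader might infer that patients consent to validation alone. Inclusion criterion 5 does not say alone, Research Data Sources names optimization, and the consent form is not shown. What remains is a mismatch in wording.

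Finally, a statistical analysis plan not shown here might define the analysis set. It could not undo a design rule that the protocol itself states.

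**Conclusion.** The point holds as a design defect. Followed as written, the plan gives primary metrics that mix model versions and describe no fixed model. This rests only on the text and on the plain reading that the model being updated is the model being scored.

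Optimism is possible, not established. It requires that some cases be scored after entering fine-tuning, which the protocol neither states nor prevents. Its size cannot be derived from the document. Under the assumed inputs above it runs from 0.5 points (10% reuse, 85% accuracy on reused cases) to 10 points (50% reuse, 100%), and it is zero under strict score-before-train order. Even a bias of 1 or 2 points would matter at this sample size.

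The matter should be settled before enrolment begins. Once cases have updated the model without a log, it may not be possible to show which results came from unseen patients.

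**What to change.** 1. Lock and version the model (weights, preprocessing, decision threshold) before the first validation patient.
2. Base every primary outcome on that version's single output for each patient, generated and stored before the case enters any fine-tuning. State this in section 3 (I) and in Statistical Analysis Procedures.
3. Keep optimization, which is a declared aim, as a separate exploratory analysis. Report each updated version on its own, only on patients enrolled after its training-data cut-off.
4. Keep a version log with the lock date, the cut-off of each update and the version behind each output.
5. Reconcile inclusion criterion 5 (validation) with Research Data Sources (validation and performance optimization).

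The cost is protocol wording, the log, and running the locked version alongside any updated one. No validation cases are lost, because the locked version can score all of the roughly 2000 patients. Exploratory updating can run in parallel, so the 12-month schedule need not depend on it. The real downside is that the headline figure gains nothing from in-study updates.

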## **(II) Study Duration**

The study duration is 12 months, officially commencing from the date of approval by the hospital's Institutional Review Board (IRB). The project is scheduled to start on November 15, 2026, and complete all case enrollment, data analysis, and result summarization by November 15, 2027, forming a comprehensive clinical prospective validation report.

## **(III) Patient Inclusion, Exclusion, and Withdrawal Criteria**

### **Inclusion Criteria**

1. Adult patients aged  $\geq 18$  years;
2. Undergoing imaging examinations (CT, MRI, ultrasound, etc.) in the hospital during the study period;
3. Examination items corresponding to the disease types or systems focused on by the study (hepatobiliary and pancreatic system);
4. Possessing at least complete imaging data and radiology diagnostic reports, with relevant medical record information as supplementary modalities;
5. Patients or their legal representatives signing an informed consent form, agreeing to the use of their de-identified data for scientific research model validation;
6. Case data passing quality review, with good imaging quality and standardized text records.

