### **Exclusion Criteria**

1. Patients refusing to sign the informed consent form;
2. Imaging data unassessable due to severe motion artifacts, incomplete scanning, or equipment malfunctions;
3. Severe lack of clinical data or inability to match with imaging data;
4. Special pathological cases or post-operative cases (e.g., extensive resection, significant structural changes after radiotherapy) that affect the consistency of model analysis;
5. Data samples with privacy protection or legal risks.

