### **Retrospective Study Phase**

We adopt the LLaVA-Med model as the base model and employ the Low-Rank Adaptation (LoRA) parameter-efficient fine-tuning strategy, with the task scenario focusing on medical image-text bimodal report generation and disease diagnosis. Since LLaVA-Med has already completed pre-training on large-scale image-text alignment data and possesses strong cross-modal alignment capabilities, the fine-tuning objective of this study mainly focuses on medical domain knowledge adaptation and enhancement of task-specific generation capabilities. In this context, most of the model's visual encoder and language backbone are kept frozen, with only the cross-modal interaction module and LoRA low-rank parameters updated, thereby significantly reducing the required data scale.

Comprehensively considering factors such as model parameter scale, number of modalities, task complexity, domain transfer span, and freezing ratio, and substituting the original pre-training scale of LLaVA-Med into empirical formulas, the effective fine-tuning sample size required for this study is estimated to be approximately 10,000–20,000 pairs of high-quality image-text samples. This sample size not only ensures stable semantic alignment and knowledge transfer between medical imaging and clinical text in the model but also balances the efficiency and resource controllability of LoRA fine-tuning.

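### The protocol speaks of newly diagnosed cases, but its operative criteria let in patients whose diagnosis is already in the record, and the diagnosis-task analysis pools them

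*Protocol*

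**What the plan says.** Two descriptions of the study population stand side by side in section 3 of the Protocol.

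- **Study Design Type and Methodology (I), design paragraph:** consecutive enrolment of newly diagnosed cases that meet the inclusion criteria.
- **Same section, phase 1, and Inclusion Criteria (III):** patients having imaging in the hospital, recruited by the pre-defined criteria. The imaging criterion is "Undergoing imaging examinations (CT, MRI, ultrasound, etc.) in the hospital during the study period". The other criteria cover age, organ system, complete images and report, consent and data quality. None concerns prior diagnosis or treatment.

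The exclusion closest to the issue is "Special pathological cases or post-operative cases (e.g., extensive resection, significant structural changes after radiotherapy) that affect the consistency of model analysis". The first withdrawal criterion refers back only to the inclusion and exclusion lists.

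Under phase 2 the model works from images and the accompanying clinical text. Research Data Sources lists "Text data from the electronic medical record system, including admission records, discharge summaries, progress notes, and surgical records". Statistical Analysis Procedures analyses all enrolled cases and takes the final clinical diagnosis or pathology as the reference for the diagnosis task.

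The sample size section plans around a contrast: "Assuming the model achieves an accuracy of approximately 85% in the disease diagnosis task", "compared with an 80% accuracy rate of manual diagnosis". The retrospective phase uses "approximately 10,000–20,000 pairs of high-quality image-text samples" for fine-tuning.

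**The concern.** A patient with a recorded hepatobiliary or pancreatic diagnosis who returns for a staging or follow-up scan meets every numbered inclusion criterion. Such a patient need not meet any exclusion. The diagnosis may already be written in text supplied to the model, and the treating clinicians already know it. A correct answer then says little about whether the model can diagnose from the examination.

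Limiting the text to what predates the index scan would not remove the problem, because an established diagnosis is legitimate earlier text.

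Two things are at stake. The headline accuracy, AUC and sensitivity can look better than they are for undiagnosed patients, to whom the diagnostic claim refers. The contrast between model and manual diagnosis can also be diluted by cases that both get right for the same uninformative reason.

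**Working it through.** **Step 1: can such patients enter?**

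| Place in the Protocol | Effect on a patient with a recorded diagnosis |
|---|---|
| 3 (I), design paragraph | Bars them if newly diagnosed means undiagnosed before the scan. Does not bar a patient diagnosed shortly before a staging scan. The term is undefined. |
| 3 (I), phase 1 | Admits; refers to the criteria list |
| 3 (III), Inclusion Criteria | Admits; no item on prior diagnosis |
| 3 (III), Exclusion Criteria, item 4 | Removes some post-operative, post-radiotherapy or special cases, if they disturb model analysis |
| 3 (III), Withdrawal Criteria, item 1 | Gives no ground for removal if the numbered lists are met |
| 3 (IV), Statistical Analysis Procedures | Pools them; the baseline variables listed do not include prior diagnosis or treatment |

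The design paragraph and the lists conflict, and the lists are what withdrawal enforces.

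**Step 2: the plan's own figure.** With 85% against 80%, two-sided alpha 0.05 and 80% power, the two-proportion formula gives

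n = [1.960·√(2·0.825·0.175) + 0.842·√(0.85·0.15 + 0.80·0.20)]² / 0.05² = 906 per group

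(one-sided: 714). The stated 500–600 per group is not reproduced. That is a separate matter and lends no support to this point. The calculation is used here only as a baseline.

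**Step 3: illustration of the mechanism.** Let p be the share of cases with a recorded diagnosis. The documents give no value, so p = 10%, 30% and 50% are assumptions. Assume also that 85% and 80% apply to undiagnosed patients and that model and clinicians both score 98% in the others.

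- Model: 85(1 − p) + 98p
- Manual: 80(1 − p) + 98p
- Difference: 5(1 − p)

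Two readings of the comparison are shown:

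- **Two groups:** 1000 per group, that is, the planned 2000 or so split in two.
- **Paired:** all 2000 diagnosed by both. Power is Φ[(d√n − 1.960√ψ)/√(ψ − d²)]. Discordance ψ is 0.85·0.20 + 0.15·0.80 = 0.29 in undiagnosed patients and 2·0.98·0.02 = 0.0392 in the others, taking errors as independent.

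| p | Model % | Manual % | Difference (points) | n per group for 80% power | Power, 1000 per group | Power, 2000 paired |
|---|---|---|---|---|---|---|
| 0% | 85.0 | 80.0 | 5.0 | 906 | 83.8% | 98.6% |
| 10% | 86.3 | 81.8 | 4.5 | 1039 | 78.5% | 97.5% |
| 30% | 88.9 | 85.4 | 3.5 | 1434 | 64.8% | 92.2% |
| 50% | 91.5 | 89.0 | 2.5 | 2209 | 47.0% | 78.7% |

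**Step 4: what if 85% and 80% already describe the enrolled mix?** Then the planned contrast is not diluted, but the accuracy in undiagnosed patients is lower than the headline. At p = 30%, the model has (85 − 0.3·98)/0.7 = 79.4% and manual diagnosis has (80 − 0.3·98)/0.7 = 72.3%. The overstatement of absolute accuracy remains.

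**The case against.** The strongest objection is that the design paragraph does state a restriction. If it is enforced, and read as undiagnosed before the scan, p is about zero and nothing is diluted. A reader might infer from the inclusion list alone that the protocol as a whole admits any known, treated patient. The documents do not support that. What stands is that the restriction is undefined and is absent from the lists that govern recruitment and withdrawal.

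Other points on that side:

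- **Exclusion 4 is wider than surgery.** Its examples are illustrative and include radiotherapy, so some other treated cases could fall under it. It still turns on disturbance of model analysis, not on whether the diagnosis is known. For this reason no claim is made here about Dice or Hausdorff results.
- **The task need not be trivial.** Records are a supplementary modality in the inclusion list, so some patients may have little text, and nothing shows that the model would simply repeat a recorded diagnosis. Trivial would be an inference. The supportable statement is that the answer can be present in the input.
- **The figures rest on assumptions.** Equal accuracy in the two readers forces the factor (1 − p). In general the difference is 5(1 − p) plus p times the model-minus-manual gap in those patients, so it shrinks only if that gap is below 5 points.
- **Power may hold up.** On the paired reading, power stays above 90% at a 30% share. The main harm is to interpretation.
- **Overlap with fine-tuning data is not shown.** It is possible at a single centre drawing on its own records, but the protocol does not say that it occurs.
- **Analysis sets may belong in the SAP, which is not at hand.** That is fair for the strata. Who is eligible, and what is recorded at enrolment, are protocol matters.

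**Conclusion.** The point holds as an unresolved conflict in eligibility with a foreseeable bias. The operative criteria do not carry the newly diagnosed restriction, and the term is not tied to the index examination. Patients whose diagnosis is already in the record can enter and are pooled with the rest.

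The expected direction is upward for absolute accuracy, AUC and sensitivity, provided that the record text reaches the model and is used. It is downward for the model-minus-manual difference, provided that both do about equally well in these patients. The size cannot be determined from the documents. Under the stated assumptions (98% for both, shares of 10% to 50%), model accuracy rises from 85% to between 86.3% and 91.5%, and the 5-point difference falls to between 4.5 and 2.5 points. These are illustrations, not estimates. The change is worth making before enrolment starts, but the protocol is not shown to enrol such patients in any particular number.

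**What to change.** 1. Reconcile the design paragraph, phase 1 and the inclusion list by defining eligibility status relative to the index examination.
2. Record at enrolment whether the target diagnosis was established, or treatment for it begun, before that examination.
3. Make patients with neither the primary set for the diagnosis task. Report the others as a separate stratum.
4. Match pseudonymised identifiers against the fine-tuning data, and remove from the primary set any patient whose earlier examination was used there.

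The cost is one enrolment field taken from records already collected, one identifier match and some wording. The downside is a smaller primary diagnosis set and a less favourable absolute accuracy.

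Under the assumptions above, the smaller set need not lose power. With p = 30%, 1400 of 2000 patients remain, and the paired calculation with d = 0.05 and ψ = 0.29 gives Φ[(0.05·√1400 − 1.960·√0.29)/√(0.29 − 0.0025)] = Φ(1.52), about 94%, against 92.2% when all are pooled. With p = 50%, 1000 remain and the same formula gives Φ(0.98), about 84%, against 78.7%.
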